## 9.5 APPENDIX 5: CHANGE HISTORY

### 9.5.1 Protocol Amendment 1

Protocol Amendment 1 was issued in order to make administrative changes, update exclusion criteria noted in the table, update references, remove preterm and term neonate information, and to provide clarification regarding meal consumption, fasting, vital signs collection, and pregnancy testing.

Protocol Section	Change	Rationale
Throughout the protocol	Minor administrative changes were made.	
Synopsis Study Design, 3. Study Design and 9.2 Appendix 2: Schedule of events	Clarification regarding beverage ingestion: ...no beverages may be ingested within 3 hours before or 3 hours after study drug administration; excluding a beverage that is being consumed as a part of the required meal.	Clarification added that beverages other than water may be ingested during 3 hours before or 3 hours after taking study drug so long as they are being consumed as part of the required meal.
Synopsis Exclusion Criteria and 4.2 Exclusion Criteria	Amended Exclusion Criteria #7: Subject has evidence or history of clinically significant allergic reaction (excluding seasonal allergies); or has evidence or history of clinically significant disease, including hematological, endocrine, pulmonary, gastrointestinal, cardiovascular, hepatic, psychiatric, or neurological disease. Exceptions to these disease criteria (e.g., stable, mild joint disease unassociated with collagen vascular disease) may be made following discussions with the medical monitor.	Clarification added to allow for subject inclusion for those that have evidence or history of seasonal allergies.

Protocol Section	Change	Rationale
Synopsis Exclusion Criteria and 4.2 Exclusion Criteria	Amended Exclusion Criteria #10: Subject is 20 years of age or older and has a $\geq 30\%$ risk of developing a myocardial infarction or coronary death within the next 10 years using the National Cholesterol Education Program's Risk Assessment Tool: https://www.mcw.edu/calculators/ldl-cholesterol-goal-level .	The risk calculator was updated in order to prevent automatic elimination of males aged 70+ years with no other risk indicators. Cardiac and pulmonary function is adequately monitored using additional inclusion/exclusion criteria. Therefore, this criteria was amended from $\geq 10\%$ risk to $\geq 30\%$ risk.
Synopsis Exclusion Criteria and 4.2 Exclusion Criteria	Removed Exclusion Criteria #32: Subject is at a high risk of contracting SARS-CoV-2/COVID-19 infection, including, but not limited to, individuals with known close contact with: 
 
Anyone residing in, visiting, or working at a health care or long-term care institution (i.e., long-term care facilities, acute care hospitals, rehabilitation hospitals, mental health hospitals, emergency departments).
 
Anyone with a known history of COVID-19 within 2 weeks prior to study entry.
 
Anyone who traveled outside the United States or has recently traveled outside of the state in which they will be enrolled in the study and has returned from a state that is listed on a travel advisory list requiring quarantine for any duration within 30 days before study entry.
 
	Because the majority of the population has been vaccinated for COVID-19 and the sites have their own guidelines in place regarding COVID-19, this exclusion criteria was removed.

Protocol Section	Change	Rationale
Synopsis Exclusion Criteria and 4.2 Exclusion Criteria	Amended Exclusion Criteria #34: Subject has previously participated in this clinical trial.	Clarification added to only prevent subject inclusion for those that have previously participated in this study. Other tecovirimat study enrollment is allowable so long as all other Inclusion/Exclusion criteria are met.
Section 4.3, Section 6.2.2 Clinical Laboratory Testing and 9.2 Appendix 2: Schedule of events	Clarification regarding fasting for fasting lipid panel: Fasting shall occur for 8 hours prior specimen collection.	Clarify amount of time subjects are required to fast prior to screening.
Section 5.2.2 Study Drug Accountability	Clarification regarding study visit requirements for study drug accountability: Subjects will be instructed to bring the subject diary and all study drug bottles (including empty bottles) and unused study drug (in study drug bottles) with them to every study visit.	Clarification for subjects to bring all bottles (including empty) and study drug to every study visit.
Section 6.2 Clinical Laboratory Testing	Clarification regarding clinical laboratory testing performed at the Central Laboratory: The following clinical laboratory assessments will be performed by the PPD Central Lab	Clarification added to clinical laboratory testing.
Section 6.2.2 Clinical Laboratory Testing	Clarification regarding pregnancy testing: All positive urine tests will be verified using a serum $\beta$ -human chorionic gonadotropin test.	Clarification added to pregnancy serum and urine testing type.
Section 8 Reference List	Reference updated for the TPOXX full prescribing information.	TPOXX prescribing information was updated.
Section 8 Reference List	Reference updated for the TPOXX investigator brochure.	TPOXX investigator brochure was updated.

Protocol Section	Change	Rationale
9.2 Appendix 2: Schedule of events	Clarification regarding vital signs testing: Vital signs will be measured within 60 minutes prior to the first dose of the day and 4 hours following the first dose of the day.	Clarification added for predose vital signs.
9.2 Appendix 2: Schedule of events	Clarification regarding pregnancy testing: A urine pregnancy test will be performed and read locally on Day -1 (PK subset) or Day 1 Predose (Non-PK subset). All other pregnancy tests, including screening, are by serum and read by the Central Lab.	Clarification added to pregnancy serum and urine testing.
9.4 Appendix 4: Division of Acquired Immune Deficiency Syndrome (DAIDS)	Remove preterm and term neonate DAIDS information: 
 
- Preterm neonates should be assessed using local laboratory normal ranges.
 
- Appendix A takes priority over the main grading table in all assessments of total bilirubin for term and preterm neonates.
 
- See Appendix A. Total Bilirubin for Term and Preterm Neonates6
 
	Reference to neonate grading and Appendix A is not applicable to this study and has therefore been removed.
Appendix 5	Added Protocol Change History.	First amendment.

## List of Abbreviations

$\lambda_z$	the observed elimination rate constant
AE	adverse event
AUC	area under the plasma concentration-time curve
AUC 0-24	area under the plasma concentration-time curve from time zero to 24 hours
AUC 0-tau	area under the plasma concentration-time curve during the first dosing interval
BID	two times a day
BLQ	below the limit of quantification
C avg	average steady-state plasma concentration
CFR	Code of Federal Regulations
CI	confidence interval
CL ss /F	apparent clearance; total systemic clearance not corrected for bioavailability (F) after multiple dosing at steady state
C min	minimum observed drug concentration in plasma
C max	maximum observed drug concentration in plasma
CRA	clinical research associate
CRF	case report form
C trough	trough plasma concentration
CV	coefficient of variation
CYP	cytochromes
DAIDS	Division of Acquired Immune Deficiency Syndrome
DSMB	Data Safety Monitoring Board
ECG	electrocardiogram
eCRF	electronic case report form
ET	early termination
FDA	Food and Drug Administration
GCP	Good Clinical Practice
ICF	informed consent form
ICH	International Council for Harmonisation
IRB	institutional review board
ITT	Intent-to treat
IWRS	interactive web response system
PK	pharmacokinetic(s)
PP	per protocol
PT	preferred term
QTcF	Fridericia-corrected QT interval

$R_{ac}$	accumulation ratio
SAE	serious adverse event
SAP	statistical analysis plan
SOC	system organ class
SOP	standard operating procedure
TLFs	tables, listings and figures
$t_{1/2}$	terminal elimination half-life
TID	three times a day
$T_{max}$	time to maximum observed plasma concentration
$V_z/F$	volume of distribution in the terminal elimination phase not corrected for bioavailability (F) after multiple dosing (D28)

## **1. Introduction**

The purpose of this statistical analysis plan (SAP) is to define and ensure that the data listings, summary tables and figures that will be produced, and the statistical methods that will be used are complete and appropriate to allow valid conclusions consistent with the study objectives. This SAP V2 dated March XX, 2023 is written based on SIGA Protocol: SIGA-246-024, version 2.0, dated 01 August 2022.

TPOXX 600 mg (3 × 200-mg capsules) two times a day (BID) for 14 days is the approved dose of TPOXX for the treatment of smallpox in patients weighing between 13 kg and less than 120 kg,. TPOXX dosing for patients weighing 120 kg or more should be adjusted to 600 mg TPOXX three times a day (TID). The 28-day TPOXX treatment duration, rather than the 14-day duration, was chosen for the postexposure prophylaxis indication as a longer treatment period may be necessary to provide protection from smallpox from the time of initial exposure to variola virus until the development of protective neutralizing antibodies. This accounts for the 7- to 17-day, asymptomatic stage; the subsequent 2- to 3-day, prodromal stage; and finally, the development of neutralizing antibodies, which are evident from about the sixth day following the onset of clinical symptoms and increase in antibody titer thereafter.

## **2. Study Objectives**

### **2.1. Primary Objective**

The primary objective of this study is to determine the safety and tolerability of TPOXX when administered orally for 28 days in adult subjects.

### **2.2. Secondary Objective**

The secondary objective of this study is to describe the PK profile of TPOXX when administered orally for 28 days in adult subjects.

## **3. Study Design and Description**

This is a Phase 3, multicenter, double-blind, randomized, placebo-controlled study to assess the safety, tolerability, and PK of oral TPOXX 600 mg when administered for 28 days in adult subjects.

A total of at least 445 subjects (includes a PK subset of 40 subjects), ages 18 to 80, inclusive, will be enrolled and randomly assigned within stratified age groups (18 to 30 years, 31 to 45 years, 46 to 64 years, and 65 to 80 years) to 1 of 2 treatment groups in an overall randomization of 4:1 (approximately 356 subjects will receive TPOXX and 89 subjects will receive TPOXX matching placebo). There will be 2 dosing regimens based on the subject's body weight: subjects with a body weight of 120 kg or less will be administered either TPOXX 600 mg or placebo two times a day (BID), 12 hours apart ( $\pm$ 30 minutes); and subjects with a body weight of more than 120 kg will be administered TPOXX 600 mg or placebo three times a day (TID), 8 hours apart ( $\pm$ 30 minutes). The study will consist of a screening period (Day -28 to Day -2), 1 check-in, on-site visits (Day 7, Day 14, and Day 21), a dosing complete/ET visit (Day 29), and 2 follow-up telephone calls (Day 42 [+2 days] and Day 58 [+2 days]). The total duration of the study for each subject, including screening, treatment, and follow-up telephone calls will be approximately 86 days,

The enrollment goal for the study is to randomly assign a sufficient number of subjects to ensure that at least 300 subjects receive at least 92% of the oral TPOXX 600 mg BID or TID dosing regimen over the 28-day treatment period. Overall, across all clinical investigative sites, a goal of approximately 20% of subjects (i.e., 89 subjects) or more will be enrolled and randomly assigned in each age group to ensure a representative investigation of TPOXX safety and PK across age groups. The treatment groups will be as follows:

- Treatment Group 1: An oral dose of 600 mg (3 × 200-mg capsules) TPOXX BID (every 12 hours [ $\pm$ 30 minutes]) for subjects with a body weight of 120 kg or less or TID (every 8 hours [ $\pm$ 30 minutes]) for subjects with a body weight more than 120 kg for 28 days (Day 1 to Day 28).
- Treatment Group 2: An oral dose of placebo (3 capsules identical to TPOXX) BID (every 12 hours [ $\pm$ 30 minutes]) for subjects with a body weight of 120 kg or less or TID (every 8 hours [ $\pm$ 30 minutes]) for subjects with a body weight more than 120 kg for 28 days (Day 1 to Day 28).

Subjects that fail to meet any inclusion or meet one or more exclusion criteria prior to study drug administration will not be randomized into the study. Under certain circumstances, a subject may be terminated from participating in the study based on the opinion of the investigator, the medical monitor, the sponsor, the Food and Drug Administration (FDA), and/or the Data Safety Monitoring Board (DSMB).

Subjects can withdraw consent and discontinue from the study at any time, for any reason, without prejudice to further treatment.

The investigator may withdraw a subject from the study for any of the following:

- Subject is in violation of the protocol.
- Subject experiences a serious or intolerable AE that in the investigator's opinion requires withdrawal from the study.
- Subject becomes pregnant.
- Subject is noncompliant.
- Subject has laboratory abnormalities for assessments listed in [Sections 4.1](#) or [Section 4.2](#) that meet grade 3 or grade 4 on the Division of Acquired Immune Deficiency Syndrome (DAIDS) AE Grading Table; any other grade 3 or grade 4 AE; or a grade 2 or higher rash considered by the investigator to be possibly, probably, or definitely related to study drug.
- Subject develops, during the course of the study, symptoms or conditions listed in the exclusion criteria.
- Subject develops laboratory abnormalities listed in the exclusion criteria during the course of the study.
- Subject requires a medication prohibited by the protocol.
- Subject requests an early discontinuation for any reason.
- Subject's primary care provider requests that the subject be withdrawn.

The FDA, SIGA, or the DSMB may request subject withdrawal based on study safety findings.

The investigator can also withdraw a subject upon the request of SIGA or if SIGA terminates the study. Upon occurrence of an SAE or intolerable AE, the investigator will confer with the medical monitor and with SIGA. If a subject is discontinued because of an AE, the event will be followed until it is resolved or stabilized as determined by the investigator and/or the medical monitor.

### **3.1. Subject Selection**

The study population will consist of male and female volunteers, aged 18 to 80 years inclusive.

#### **3.1.1 Inclusion Criteria**

As stated in Protocol Section 4.1.

#### **3.1.2 Exclusion Criteria**

As stated in Protocol Section 4.2.

### **4. General Statistical Considerations**

All statistical analyses will be conducted using statistical analysis system SAS® Version 9.4 or higher (SAS Institute, Cary, NC).

Descriptive statistics for continuous variables will include number of subjects, mean, standard deviation (SD), median, minimum, and maximum, unless otherwise noted. For categorical variables, frequencies and percentages will be presented.

All tables, listings, and figures will be presented by treatment and weight. The treatments below will be used for presentations:

- TPOXX 600mg
- Matching TPOXX Placebo

Unless otherwise indicated, outputs which are summarized by treatment and weight will be summarized for each dose level for subjects on active study drug.

All data listings will be sorted by treatment (TPOXX or placebo), by treatment regimen (BID or TID dosing), and subject number.

### **Visit Windows**

There are no plans to derive visit windows; visits will be used in the analyses as reported on the eCRF.

### **Pooling of Sites**

Up to 10 sites in the USA will be used in this study. The PK subset will be enrolled at 1 Phase 1 unit. For the remaining sites, a maximum number of subjects will be agreed upon and enrollment

will be competitive. Thus major differences in subject enrollment numbers per site are not expected, and therefore there will be no inter-subject pooling of data.

## **Subgroups**

The effects of age group (18 to 30 years, 31 to 45 years, 46 to 64 years, and 65 to 80 years) used for stratification at randomization and site will be investigated for AE and severe AE rates. Time to first AE or severe AE and time to withdrawal for any reason will be calculated.

Study day is relative to first dose of study drug. Study days are calculated with respect to the first dose date as below:

- If the assessment/observation date is on or after the first dose date, then Study Day = Assessment/Observation Date – First Dose Date + 1;
- Otherwise, Study Day = Assessment/Observation Date – First Dose Date.

Baseline will be defined as the last non-missing assessment (including repeated and unscheduled assessments) before the first dose of study drug administration, unless otherwise specified.

For summary of safety assessments, if there are repeated measurements at a time point, the first non-missing assessment at that time point will be used in the summary tables.

Unscheduled results will not be included in the summary tables, except for determining Baseline, but will be presented in data listings.

The methodology and data handling specifications for PK data are detailed in [Section 8](#).

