#### **4.4.3 Halting Rules**

Safety evaluations will include: medical history, body weight, physical assessments, vital sign measurements, routine laboratory test results, ECG results, and AEs reported by

subjects. Symptom-directed or targeted physical examinations may be performed if indicated by interim complaints or laboratory findings.

The medical monitor and investigator will closely monitor and analyze study data as they become available and will make determinations regarding the presence and level of AEs. The medical monitor will provide an independent review of the AEs that have a bearing on study stopping. All AEs determined by the investigator to be severe and possibly, probably, or definitely related to study drug, as well as all clinical assessments, laboratory test results, ECG results, or vital sign measurements that meet grade 3 criteria on the DAIDS AE Grading Table will be assessed by the medical monitor, who will make a recommendation as to whether or not temporary halting of the study should occur.

The study will be temporarily halted (no new enrollments and no further study drug dosing) by the medical monitor or designee by promptly notifying the investigators and the DSMB (as outlined in the DSMB charter) according to the following criteria:

- One subject experiences a grade 4 AE assessed as possibly, probably, or definitely related to study drug.
- There is a subject death that is assessed as possibly, probably, or definitely related to study drug.
- One subject experiences a seizure that is assessed as possibly, probably, or definitely related to study drug.
- Two or more subjects experience the same or similar SAEs that are possibly, probably, or definitely related to the study drug.
- Three or more subjects experience the same or similar AEs that are DAIDS grade 3 or above and are possibly, probably, or definitely related to the study drug.
- Three or more subjects have clinically significant laboratory abnormalities that meet DAIDS grade 3 or above criteria.

Investigators will advise SIGA immediately if any of the halting rules are met and SIGA will notify the FDA immediately.

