## **6.2 SAFETY ASSESSMENTS AND ENDPOINTS**

Safety and tolerability will be assessed by the following endpoints: monitoring and recording of AEs; clinical laboratory test results (hematology, serum chemistry, and urinalysis); pregnancy testing; vital sign measurements (systolic and diastolic blood pressures, heart rate,

respiratory rate, and body temperature); 12-lead ECG results; and physical examination findings. A blood sample will be collected for all subjects who discontinue from the study for TPOXX plasma concentration analysis *if the ET visit occurs within 30 hours after the subject's last dose of TPOXX/matching placebo* in order to collect information about the relationship between TPOXX blood level and ET from the study.

For all safety assessments, the investigator will determine whether results are clinically significant, which is defined as any variation in a result that has medical relevance and may result in an alteration in medical care (e.g., active observation, diagnostic measures, or therapeutic measures). If clinical significance is noted, the result and reason for significance will be documented and an AE will be reported on the AE page in the subject's eCRF. The investigator will monitor the subject until the result has reached the reference range or the result at screening, or until the investigator determines that follow-up is no longer medically necessary.

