## 6.2.2 Clinical Laboratory Testing

Blood and urine samples will be collected at the time points indicated in the schedules of events (Table 9-1 and Table 9-2) and will be prepared using standard procedures. Samples for safety testing will be shipped via courier to PPD Central Lab where they will be analyzed. The central laboratory for the study will receive, test, and store laboratory safety samples at the following location:

Repeat clinical laboratory tests may be performed at the discretion of the investigator, if necessary, to evaluate inclusion and exclusion criteria or clinical laboratory abnormalities. PPD Central Lab will provide the reference ranges for all clinical laboratory safety parameters.

The following clinical laboratory assessments will be performed by the PPD Central Lab:

Hematology	Hematocrit, hemoglobin, mean corpuscular hemoglobin, mean corpuscular hemoglobin concentration, total and differential leukocyte count (basophils, eosinophils, lymphocytes, monocytes, neutrophils), mean corpuscular volume, platelet count, red blood cell count, and red cell distribution width
Serum Chemistry	Alanine aminotransferase, albumin, alkaline phosphatase, anion gap, aspartate aminotransferase, bilirubin (total), blood urea nitrogen, calcium, carbon dioxide, chloride, creatinine, creatinine clearance (calculated (a) ), gamma-glutamyltransferase, globulin, glucose, lactate dehydrogenase, phosphorus, potassium, sodium, total protein, and uric acid
Urinalysis	Appearance, bilirubin, blood, color, glucose, ketones, leukocyte esterase, microscopy (performed if dipstick is $\geq 1+$ ; includes bacteria, casts, crystals, epithelial cells, red blood cells, and white blood cells), nitrites, pH, protein, specific gravity, and urobilinogen

(a) Creatinine clearance will be calculated using the Cockcroft-Gault formula:

$$\text{Creatinine clearance (mL/min)} = \frac{[140 - \text{age (years)}] \times \text{weight (kg)}}{72 \times \text{serum creatinine (mg/dL)}} \{ \times 0.85 \text{ if female} \}$$

Glycosylated hemoglobin and a fasting lipid panel including cholesterol (total, high-density lipoprotein, calculated low-density lipoprotein, and triglycerides) will be performed at

screening. Subjects will fast for 8 hours prior to specimen collection of the fasting lipid panel.

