Time from the first dose to the first AE or to discontinuation from study for any reason will be analyzed using Kaplan-Meier quartile estimates along with 2-sided 95% CIs. Treatment groups will be compared using the log rank test stratified by age group and site. If a subject does not experience any AE or does not discontinue from study, the time to first AE or time to discontinuation will be censored at the date of study completion.

Toxicity grades for laboratory tests will be determined according to the DAIDS AE Grading Table. The maximum postbaseline grade increase from baseline grade will be summarized by treatment group and BID and TID study drug dosing regimen and overall for the Safety Population and PP Safety Population using frequency and percentage of subjects with increase to grade 1, 2, 3, 4, 1 to 4, 2 to 4, and 3 to 4, respectively.

Actual values and changes from baseline for clinical laboratory test results, vital sign measurements, and 12-lead ECG results will be summarized by treatment group and BID and TID study drug dosing regimen at each time point using descriptive statistics (number of subjects, mean, SD, median, minimum, and maximum). Shift tables will be generated for clinical laboratory test results. Physical examination findings will be presented in a data listing.

Narratives will be presented for all deaths, subjects who reported SAEs, subjects withdrawn because of AEs, and grade 3 AEs deemed by the investigator to be possibly, probably, or definitely related to study drug.

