- AEs by maximum severity, overall and by system organ class and preferred term
- AEs by maximum relationship to study treatment, overall and by system organ class and preferred term
- Treatment-related AEs, overall and by system organ class and preferred term
- Serious AEs, overall and by system organ class and preferred term.

In general, all AE tables will show the number and percentage of subjects with an event. The number of events overall by treatment group and dosing regimen will also be included.

A listing of all AEs will provide details including system organ class, preferred term, verbatim term, whether treatment was emergent or not, severity, relationship to treatment, onset and resolution date and time, duration (in days for any AEs lasting longer than 24 hours, in hours otherwise, derived as stop date and time – start date and time), action and outcome. Similar listings will be presented for SAEs, AEs with Grade 3 or higher, AEs with a fatal outcome (or Grade 5) and AEs leading to early withdrawal.

Toxicity grades for laboratory tests will be determined according to the [DAIDS AE Grading Table](#). The maximum post-baseline grade increase from baseline grade will be summarized by treatment group and dosing regimen and overall for the safety population and PP safety population using frequency and percentage of subjects with increase to grade 1, 2, 3, 4, 1 to 4, 2 to 4, and 3 to 4, respectively.

All AEs will be presented in a data listing.

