### **9.8. Unscheduled Visits**

Clinical investigative sites will provide subjects with the contact information for the study site personnel. Subjects are free to contact study site personnel at any time, and the clinical investigative site may require an unscheduled visit for the purpose of physical examinations, laboratory tests, etc. Unscheduled visits will be documented by study site personnel in the source document. Unscheduled procedures and laboratory tests and results will also be recorded in the eCRF.

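### The maximum post-baseline laboratory grade table excludes unscheduled results, so it can understate a subject's worst DAIDS grade

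*Combined protocol and SAP*

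**What the plan says.** SAP section 4 sets a general rule for safety outputs: "Unscheduled results will not be included in the summary tables, except for determining Baseline, but will be presented in data listings". Baseline is the only exception. The sentence before it deals with repeats at a time point: "the first non-missing assessment at that time point will be used in the summary tables".

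SAP section 9.3.3 then plans the laboratory toxicity summary: "The maximum post-baseline grade increase from baseline grade will be summarized by treatment group and dosing regimen and overall". The protocol plans the same output in section 7.3.2: "The maximum postbaseline grade increase from baseline grade will be summarized by treatment group". Neither text limits the maximum to scheduled visits, and neither brings unscheduled results back in.

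The protocol foresees laboratory tests outside the schedule. Section 6.2.2 says "Repeat clinical laboratory tests may be performed at the discretion of the investigator", for eligibility or to evaluate abnormalities, and section 6.2.7 allows unscheduled visits with laboratory tests. The data are captured. SAP section 9.8 says "Unscheduled procedures and laboratory tests and results will also be recorded in the eCRF".

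**The concern.** A table labelled as the maximum post-baseline grade is read as the worst value seen. Under the general rule it would be the worst value at scheduled visits. The draws left out are often those prompted by a suspected problem, which is when a worst-grade table is most useful. Handling is also uneven: an unscheduled result can set the baseline grade, but the same kind of result cannot count after dosing.

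Safety is the primary objective, and this table is the plan's numeric summary of laboratory toxicity that does not depend on the investigator's judgement of clinical significance. At stake are its counts and percentages by treatment group.

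**Working it through.** The plan attaches no figure to this summary, so there is none to reproduce. The check is a reading of the rules, followed by a worked example.

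**1. Is there an exception?** SAP section 4 excludes unscheduled results and excepts Baseline only. SAP sections 9.3.3 (maximum grade), 9.4 (laboratory evaluations), 9.8 (unscheduled visits) and 11 (changes in the planned analysis) add no other exception. Nor does protocol section 7.3.2.

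**2. What is left?** The schedules of events give four post-baseline laboratory draws: Day 7, Day 14 (Day 13 in the PK subset), Day 21 and Day 29/early termination. None is scheduled after Day 29.

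**3. Direction.** The scheduled draws are a subset of all draws, so for each subject max(scheduled) ≤ max(all). Across subjects, the cumulative categories (grades 1 to 4, 2 to 4 and 3 to 4) can therefore only be undercounted. A single-grade category can move either way: a subject whose true worst grade is 2 may be counted under grade 1.

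**4. Can a graded value really be missed?** Hypothetical non-PK subject: a man aged 40, 80 kg, baseline creatinine 0.80 mg/dL, with one unscheduled draw on Day 16.

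- Male upper reference limit implied by protocol exclusion criterion 26: 1.7 / 1.3 = 1.31 mg/dL.
- Cockcroft-Gault (protocol section 6.2.2): (140 − 40) × 80 / (72 × creatinine) = 8000 / (72 × creatinine).
- DAIDS grade 2 (protocol Appendix 4): creatinine rising to 1.3 to <1.5 times baseline, or clearance falling by 10 to <30% from baseline.

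| Draw | Creatinine (mg/dL) | Ratio to baseline | Clearance (mL/min) | Change | Grade |
|---|---|---|---|---|---|
| Baseline | 0.80 | 1 | 138.9 | – | none |
| Day 14 | 0.82 | 1.025 | 135.5 | −2.4% | none |
| Day 16, unscheduled | 1.10 | 1.375 | 101.0 | −27.3% | 2 |
| Day 21 | 0.84 | 1.05 | 132.3 | −4.8% | none |

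The Day 16 value is 1.10 / 1.31 = 0.84 of the upper reference limit. It is therefore not flagged high, because flagging in section 6.2.2 uses the reference range. It is also below the lowest limit-based grade, which starts at 1.1 × 1.31 = 1.44 mg/dL. All clearances stay above 90 mL/min, so the absolute clearance criterion adds no grade. If Days 7 and 29 are also ungraded, the table records no increase where the data show grade 2.

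**5. Size.** If a true proportion p of subjects reach a cumulative category, and a share u of them do so only at draws left out, the table shows p(1 − u). The documents give no information on u, so no rate is offered.

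**The case against.** **The rule may be meant only for by-visit tables.** That is possible, and it is the likelier reading of the neighbouring rule on repeats, which is worded by time point. The sentence on unscheduled results has no such limit, and a programmer following it would drop them. If the sponsor intends otherwise, a sentence is still needed.

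**Other safeguards catch what matters.** Largely true, and this sets the severity. For a clinically significant result, "the result and reason for significance will be documented and an AE will be reported on the AE page"; the AE is then graded on DAIDS and tabulated by maximum severity. Laboratory results "that meet grade 3 criteria on the DAIDS AE Grading Table will be assessed by the medical monitor". Protocol section 4.4.3 has a halting criterion for clinically significant abnormalities of grade 3 or above in three or more subjects, and section 9.3.3.1.4 requires immediate DSMB notification of clinically significant grade 4 abnormalities. SAP section 15 lists results of toxicity grade 1 or higher. But the AE route and those two DSMB and halting provisions depend on clinical significance, the medical monitor route starts at grade 3, and listings give no frequencies by group.

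**The example is contrived.** It gives no reason for the Day 16 draw. In the ordinary case, a repeat prompted by an abnormal scheduled value, the scheduled value is already in the table and information is lost only if the repeat is worse. That is fair. The example shows that a miss can happen, not how often.

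**Scheduled-only maxima give completers in both arms the same number of looks.** This stands as a trade-off. Discretionary draws give more chances of a high maximum to subjects who are tested more. The downward direction holds for each subject's maximum and says nothing about the direction of any error in the between-group comparison.

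**Conclusion.** The concern holds, as a minor one. As written, the SAP feeds the maximum-grade table from four scheduled draws per completing subject, and a higher grade seen only at another draw is left out. The conclusion rests on applying the section 4 sentence literally. The direction for each subject's maximum follows with no further assumption, and the number of subjects affected is unknown.

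The likely loss is lower-grade excursions not judged clinically significant, in one secondary descriptive table. The rule on repeats may add to it if it too is applied beyond by-visit summaries. The primary AE-rate analysis is not touched.

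**What to change.** Keep the section 4 rules for by-visit descriptive summaries, and say that this is their scope. Add to SAP section 9.3.3:

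> The maximum post-baseline DAIDS grade uses all post-baseline laboratory results, including unscheduled and repeat assessments, up to a prespecified cut-off.

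A cut-off is needed because protocol section 6.2.1 leaves follow-up of clinically significant abnormalities open-ended, and no draw is scheduled after Day 29. The end of AE collection, Day 42 (+2 days), is one option and matches the AE window, but it admits some values from selected subjects only. The Day 29/early termination visit avoids that at the price of losing later results. Either will do if fixed before unblinding. A scheduled-only maximum alongside would show how far discretionary testing drives the counts.

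Separately, the SAP section 14 index lists no toxicity-grade summary table. Add entries for both safety populations so that the promised output is produced.

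The cost is one SAP sentence, minor programming and the index entries. No new data are needed, because unscheduled results are already in the eCRF.
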